5.3.3 Treatment Duration

The Avmacol tablets will be administered to study participants for a total duration of 12 months. Data regarding the duration of SF administration on altering cellular

markers in human bronchial tissues are lacking. In a recent phase 2 clinical trial lasting 2-8 weeks, Atwell *et al.* evaluated the effect of SF on level of Ki-67 LI in breast benign tissue in women who underwent diagnostic biopsy and surgical treatment for breast cancer. The daily dose of 513 micromole glucoraphanin (SF precursor) significantly reduced Ki-67 expression in the benign breast tissue ($P<0.01$) (16). We note the conversion rate for this formulation of glucoraphanin to SF was not determined by the authors (16). It is likely lower than our Avmacol formulation: typically 5% in the absence of myrosinase. Our Avmacol tablets provide optimal internal dose of SF on apoptosis/proliferation markers, by pushing the duration of SF administration to 12 months.

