7.1.1 Adverse Events for Broccoli Sprout Preparation Avmacol®

There is no recognized risk from administration of Avmacol® tablets. The previous studies using broccoli sprout beverages in humans reported that the most common adverse events (AEs) or complaint by study participants was bad taste. As a tablet formulation, Avmacol will overcome the bad taste. Other expected AEs in gastrointestinal system are nausea and flatulence. Table 3 summarizes reported AEs in previous studies involved more than 500 study subjects.

There may be adverse events or side effects that are currently unknown. Everyone taking part in the study will be monitored carefully for any side effects, including routine physical examinations, complete blood count (CBC), blood chemistry including liver function test, and food intolerances. All AEs and toxicity measures will be evaluated as one of the objective of the present study.

Table 3. Summary of Reported Adverse Events (AEs) in Studies Using Sulforaphane or Sulforaphane Precursor Glucoraphanin in Humans

Study (reference)*	Design	Subjects	Dose*	Treatment duration	AEs																		
Kensler et al(32)	Randomized placebo-controlled phase 2 study	200 healthy volunteers	400 µmol glucoraphanin (GR)/day in hot water infusion of broccoli sprouts	14 days	No reported AEs																		
Shapiro et al(31)	Randomized placebo controlled phase I study	12 healthy volunteers	75-100 µmol GR/day	7 days	No clinical AEs; No abnormal chemistry test results. 2/12 subjects had ALT >1x ULN (grade 1 toxicity). Note: ALT level rose for all subjects including placebo-treated ones																		
Corblatt et al(29)	Single arm study	8 women undergoing elective mammoplasty	150 µmol SF	Single dose	Well tolerated, no any AEs or complications																		
Egner et al(46)	Randomized placebo-controlled phase 2 study	50 healthy volunteers	Broccoli sprout extract (BSE) beverage: 800 µmol GR/day	7 days	No AEs observed																		
Egner et al(17)	Randomized placebo-controlled phase 2 study	267 healthy volunteers	BSE beverage: 600 µmol GR + 40 µmol SF per day	84 days	10 participants (6 in BSE and 4 in placebo arm) reported grade 1 AEs: bad taste and mild stomach discomfort. One subject (in BSE) reported vomiting. Clinical values of 13 analytes of blood chemistry and liver function test for all participants at the last day of the intervention were all normal.																		

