7.1.2 Risks Associated with Study Procedures

7.1.2.1 Bronchoscopy

Bronchoscopy is very safe, but no procedure is entirely free of potential risk. The following is a description of the risks of the procedure. In recent publications, the incidence of serious complications was less than 0.05% (5 in 10,000) in over 23,000 bronchoscopies. Local discomfort (coughing, gagging and soreness of your nose and throat) are frequently unavoidable but can be greatly diminished with adequate anesthesia. Bronchitis is common after bronchoscopy and may resolve spontaneously or with antibiotic treatment. Nosebleed, wheezing (about 1% chance), a decrease in blood oxygen content of approximately 10% for approximately one half hour, low grade fever (less than a 5% chance), and lung infection (pneumonia) in less than 0.1% and slight expectoration of small flecks of blood for 24 hours after the procedure (as a result of minor trauma to the bronchial lining) may occur. More serious complications such as major bleeding, lung collapse, vocal cord and bronchial spasm, and cardiac irregularity have been reported but are very rare. Since the patient will be medicated for this procedure they will need to make arrangements for someone to drive them home.

A Bronchoscopy Patient Communication Log Form is attached (Appendix 9) to follow-up the patients after the bronchoscopy is performed. Patients are called within 24 hrs., 72 hrs., and instructed to call within 30 days, if febrile, or with increased sputum production, or increasing shortness of breath or any perceived deterioration of respiratory condition.

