9. STATISTICAL AND SAMPLE SIZE CONSIDERATIONS

This is a randomized, double blind, placebo-controlled study to evaluate the efficacy of SF as a chemopreventive agent. Eligible subjects are former smokers with ≥ 30 pack-years smoking history who quit smoking < 15 years, and are considered at high risk for developing lung cancer. The proposed duration of therapy will be 12 months for each subject. The primary objective of this trial is to assess whether oral SF supplementation elicits an increased histologic response when compared to placebo in this population over a 12-month treatment period. The planned sample size is 72 subjects (36 per treatment arm). A block randomization scheme will be used to ensure that both treatment and placebo group have the same proportion of men and women, respectively. The randomization will be done at the UPMC Hillman Cancer Center.

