9.4 Statistical Analysis for Adverse Events and Toxicity Measures

The frequencies of adverse events (AEs) and toxicity measures (e.g., CBC, liver function test, body weight) will be compared between the SF treatment and placebo arm. The analysis will be conducted for total AEs and specific AEs, expected AEs and unexpected AEs, AEs by grade and attribution grouping, respectively, at each clinical visit as well as the summed total over 4 time points of the entire treatment period. We will repeat the same analysis on a patient level. Chi-square test will be used for comparing the frequencies between the two treatment groups.

Sample Size Consideration. As described in Table 3 above, the frequencies of AEs reported were low in previous studies. Based on the frequencies reported by Atwell et al, the frequency of total AE in placebo was 33% (9 out of 27 participants), the proposed study with a total of 72 subjects will have an 80% statistical power to detect a doubled frequency (67%) of total AEs in the SF-treatment group. The proposed study can detect a less excess AE rate between the two treatment groups if all AEs over different time points are combined or all AEs are counted independently.

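### The adverse-event power in 9.4 is computed correctly, but its 33% placebo rate comes from a 2-8 week trial and fits neither the 3-month nor the 12-month window analysed here

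*Combined protocol and SAP*

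**What the plan says.** Section 9.4 plans to compare adverse events (AEs) at each clinical visit, summed over the four time points, and at patient level. The breakdowns are total and specific, expected and unexpected, by grade and by attribution. The method is given as "Chi-square test will be used for comparing the frequencies between the two treatment groups".

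The sample-size paragraph takes its placebo rate from the breast-biopsy trial, "the frequency of total AE in placebo was 33% (9 out of 27 participants", and concludes that "the proposed study with a total of 72 subjects" has "80% statistical power to detect a doubled frequency (67%) of total AEs in the SF-treatment group". It closes by saying that a smaller excess is detectable if AEs from different time points are combined or all AEs are counted independently. It does not say which time window the 33% and 67% refer to.

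Section 5.3.3 describes the source trial: "In a recent phase 2 clinical trial lasting 2-8 weeks". Table 3 (7.1.1) gives the same duration and its population, 54 women with abnormal mammograms. For the 84-day beverage trial Table 3 reports "10 participants (6 in BSE and 4 in placebo arm) reported grade 1 AEs"; section 4.1.6.2 gives that trial's arms as 136 treated and 131 placebo. Section 9 sets treatment at 12 months and states "The planned sample size is 72 subjects (36 per treatment arm".

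**The concern.** The share of patients with at least one AE accumulates with follow-up, so it means little without a window. Section 9.4 carries a share observed over 2-8 weeks into a trial with visit windows of about 3 months and a 12-month total, and makes no adjustment. The population differs too: section 3.1 enrols people aged 55-74 with airflow obstruction and/or emphysema. They have a bronchoscopy at the end of treatment, and section 7.1.2.1 notes that "Bronchitis is common after bronchoscopy and may resolve spontaneously or with antibiotic treatment". Section 7.2 counts AEs whether or not they are thought drug-related.

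The protocol's other evidence points the opposite way. The 84-day trial, close to one visit window, had a placebo rate about one-eleventh of 33%. Section 9.4 itself calls earlier AE frequencies low.

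Safety and toxicity is a stated aim (section 1.2), and the DSMB compares AE frequencies between arms (7.4). A non-significant comparison of total AEs, backed by a stated 80% power, could be read as more reassurance than the trial can give.

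**Working it through.** **Inputs.** Placebo 9/27 = 33.3%, SF 67%, 36 per arm (sections 9 and 9.4). Section 9.4 states neither alpha nor a continuity correction; I take two-sided 0.05, as in 9.1, and the uncorrected chi-square. Planned completers: 60, or 30 per arm (9.1). The 84-day trial: 4/131 = 3.1% on placebo.

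**1. The plan's own figure.** The usual formula with p1 = 1/3, p2 = 2/3 and mean 1/2 gives

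n per arm = [1.96·√(2·½·½) + 0.842·√(2/9 + 2/9)]² / (1/3)² = (1.386 + 0.561)² · 9 ≈ 34.1, so 35 per arm (70 in all, against 72).

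Exact power sums Bin(i; n, p1)·Bin(j; n, p2) over all tables with X² > 3.84, where X² = 2n[i(n−j) − j(n−i)]² / [n²(i+j)(2n−i−j)]. For n = 36 this is **81.2%**, so the stated 80% reproduces. It is 75.6% with 30 per arm, and 73.8% with 36 per arm under Fisher's test or Yates' correction.

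**2. What each source implies for this trial's windows.** Both extrapolations assume a constant hazard, which the documents do not establish.

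- Breast-biopsy trial, 33.3% reached at w weeks: rate at t weeks = 1 − (2/3)^(t/w). At 13 weeks this is 93%, 65% and 48% for w = 2, 5 and 8. At 52 weeks it is over 99.9%, 98.5% and 93%.
- 84-day trial: 3.1% over roughly one visit window; at 12 months 1 − (127/131)^(365/84) = 12.6%.

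Neither source gives 33% for either window. Sampling error alone is also wide: the exact 95% interval for 9/27 is 17% to 54%.

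**3. Consequence for power.** Exact, uncorrected chi-square, two-sided 0.05:

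| Placebo rate | Power for a doubling, 36 per arm | SF rate for 80% power, 36 per arm | SF rate for 80% power, 30 per arm |
|---|---|---|---|
| 3.1% | 7% | 23% | 26% |
| 12.6% | 27% | 41% | 44% |
| 20% | 47% | 51% | 54% |
| 33.3% | 81% | 66% | 68% |
| 40% | 95% | 73% | 75% |
| 50% | about 100% (67% is no longer a doubling) | 80% | 83% |
| 80% | a doubling cannot occur | 98% | 99% |

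With 36 per arm, some SF-arm rate gives 80% power until placebo reaches about 85% (about 82% with 30 per arm). At 90% on placebo, power is 49% even if every SF patient has an AE.

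**4. Counting AEs independently.** A chi-square test on pooled events treats repeated AEs in one patient as separate observations. To illustrate, take four visits per patient, hence 36 · 4 = 144 patient-visits per arm. With within-patient correlation ρ the effective number is 144/(1 + 3ρ): 144 at ρ = 0, about 76 at ρ = 0.3, and 36 at ρ = 1. These values of ρ are assumptions. The gain the plan claims depends on ρ, and an unadjusted test also rejects too often when ρ is above zero.

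**The case against.** Four points can be made for the plan.

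- **The calculation is right.** This stands. The fault lies in the input, and a reader who infers a computing error would be wrong.
- **The 12-month window is not stated.** Because 9.4 treats combined time points as a separate case, 33% may be meant for one visit. This is a fair reading, and it narrows the gap without closing it. A 3-month window is still longer than 2-8 weeks, and the 84-day trial, the cited placebo-controlled trial closest to that length, had 3.1%.
- **The high extrapolations are speculative.** This also stands. One might infer that nearly every placebo patient will have an AE, so that the comparison is bound to fail. The documents do not support that: 93% and above needs a constant hazard, and by the same assumption 33% at 8 weeks would be 1 − (2/3)^(12/8) = 46% at 12 weeks, against the 3.1% seen in the 84-day trial. Populations and AE capture may differ, so neither figure settles the matter. For placebo rates of 33% to 50% a doubling has at least 80% power, and combining time points can lower the detectable ratio, for instance to 80/50 = 1.6 at a placebo rate of 50%.
- **More sensitive contrasts are already planned.** Section 9.4 includes expected and attributed AEs, and 8.3.4 describes expected events as gastrointestinal. This stands, but none of these contrasts has a stated detectable effect; the only power given is for total AEs.

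**Conclusion.** The point holds as a matter of an unsupported input. The 80% is correct for 33% v 67% with all 72 subjects and an uncorrected test, but the documents justify 33% for neither the visit window nor the 12-month total. Over placebo rates of 3.1% to 40%, power for a doubling runs from 7% to 95%. Above 50% a doubling is ruled out, while smaller ratios remain detectable up to about 85%. These powers assume two-sided 0.05; the placebo range rests on the protocol's two sources, with a constant hazard wherever they are extrapolated.

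The stronger conclusion, that the stated power is unattainable in this trial, does not follow, because no 12-month placebo rate is given. Nor is the sample size in doubt: the 72 comes from the dysplasia-index calculation in 9.1. What is at stake is how a null safety comparison will be read. The claim about counting AEs independently has no valid basis as written.

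**What to change.** In 9.4:

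1. Replace the single 33%/67% statement with the detectable SF-arm rate for a named window over a range of placebo rates, for 72 and for 60 subjects, as in the table above. State alpha, sidedness and whether the chi-square is corrected.
2. Delete the claim about counting AEs independently. Compare event counts with a patient-level rate model that allows overdispersion (negative binomial, for example). The documents give no AE rate per patient-year and no dispersion, so any detectable rate ratio should be labelled as resting on assumptions.
3. Make the already planned expected (gastrointestinal) or attributed AE contrast, at patient level, the headline safety comparison, and keep total AEs as supporting description.

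The cost is a short recalculation and revised wording. The stated detectable effect becomes less favourable. No new data are needed and the sample size does not change.

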9.1 Statistical Analysis for histological responses

Endobronchial histology scores will be first summarized within each bronchoscopy by using 3 separate endpoint measures pre and post treatment respectively: 1) dysplasia index (DI, number of biopsies with dysplasia/total number of biopsies x 100), 2) average of all histological scores (all biopsies scores/number of biopsies), and 3) worst biopsy score. The 3 summary end points will be analyzed within 4 different biopsy site groupings: all biopsies, biopsies from the 6 standard endobronchial sites only, site-matched biopsies from both bronchoscopies, and site-matched biopsies where the baseline biopsy is non-normal. For each patient, the mean of each of endpoints separately for each of biopsy site groupings pre and post treatment are then calculated. The primary endpoint is the dysplasia index (DI), which has a binomial distribution with at least 6 “trials” (i.e., 6 predetermined biopsy sites), and will be analyzed by generalized estimating equations (GEE) that constrains average baseline DI to be the same for both treatment and placebo groups, and tests whether average follow-up DI differs between the SF treatment and placebo groups. All other endpoints and biopsy site groupings are secondary endpoints. The primary analysis for the average and worst dysplasia scores will be a linear regression that assesses the difference in post-treatment scores by the two treatment groups, controlling for the same scores at pre-treatment. This analysis of covariance (ANCOVA) approach has optimal efficiency in a study design to assess the pre- and post-treatment measures with high within-subject correlation due to repeated measures (80). No interim analyses for futility or superiority will be performed, other than ongoing safety monitoring.

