Sample size consideration. In the iloprost trial, 57 former smokers were randomized to receive oral iloprost or placebo for 6 months. Treatment effects (adjusted for baseline levels) were statistically significant ($P \leq 0.01$) for all 3 endpoints (dysplasia index, average dysplasia score, worst dysplasia score). Anticipating a 20% dropout rate over 12 months, we will randomize at least 72 study subjects to ensure that 60 subjects complete our SF study. Assuming an average baseline dysplasia index of 22% and post-therapy 11% for subjects receiving SF, a simulation with 10,000 trials with a sample size of 60 subjects has yielded an 80% statistical power to detect a statistically significant (two-sided $p < 0.05$) treatment effect, using generalized linear models (binomial family, 6 biopsies) after controlling for baseline levels of DI. Calculations are similar for other endpoints, and actual power should be greater than the DI measure because they are continuous measures and have observed within-subject correlation (i.e., repeated measures).

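### The chi-square on adverse events summed over visits or counted one by one ignores clustering within patients, so its p-values are too small if events are positively correlated within patient

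*Combined protocol and SAP*

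**What the plan says.** Section 9.4 analyses AEs in total and by type, expectedness, grade and attribution, "at each clinical visit as well as the summed total over 4 time points of the entire treatment period". The only test named is this: "Chi-square test will be used for comparing the frequencies between the two treatment groups". The section then adds "We will repeat the same analysis on a patient level", so the preceding comparison is on some other unit, namely events or visit records.

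The power paragraph takes a placebo rate of 33% (9 of 27 participants in the breast-biopsy study of Table 3) and states 80% power to detect 67% with 72 subjects. It ends by saying that a smaller excess can be detected "if all AEs over different time points are combined or all AEs are counted independently". Section 9.4 gives no significance level and no method for several events from one patient.

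Section 5.5 has AEs collected from every patient at each three-monthly visit. Section 9.1 uses generalized estimating equations for the dysplasia index and refers to "high within-subject correlation due to repeated measures" for the histology scores.

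**The concern.** The Pearson chi-square takes its variance from independent units. Four visit records from one patient, or several complaints from one patient, are not independent if some patients are more prone to AEs than others. The test then understates the variance of the arm difference, and its p-values are too small.

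Safety is a secondary aim (listed under section 1.2), and section 7.4 has the DSMB compare AE frequency between arms. A few patients with recurrent or multiple complaints could produce a nominally significant arm difference, in either direction, that is only clustering. The last sentence of 9.4 also presents independent counting as extra sensitivity without saying that the gain depends on the correlation.

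**Working it through.** **Inputs.** From the documents: 36 per arm (section 9), four post-baseline visits (sections 5.5 and 9.4), per-patient AE rate 1/3 (section 9.4). Assumed: two-sided 5%, because 9.4 states no level and 9.1 uses that one; complete follow-up; a range of intraclass correlations (ICC), because none is given.

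**1. The plan's own figure.** For 1/3 v 2/3 with 36 per arm, the pooled two-proportion formula is power = Φ((|d| − 1.96·√(2·p̄·(1−p̄)/n)) / √((p₁q₁ + p₂q₂)/n)). This gives Φ((0.3333 − 1.96 × 0.1179)/0.1111) = Φ(0.92) = 82%. Exact enumeration of the uncorrected chi-square gives 81.2%. The stated 80% reproduces. It is a patient-level figure and is not affected.

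**2. One yes/no record per patient-visit, pooled over four visits.** The variance is inflated by 1 + (4 − 1)·ICC. The true two-sided error of a nominal 5% test is 2·(1 − Φ(1.96/√(1 + 3·ICC))). In the simulation (beta-binomial, 40,000 trials per cell), the per-visit rate was set so that 1/3 of patients have any AE over 12 months: 0.096, 0.111, 0.143 and 0.182 for the four rows.

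| ICC | Variance factor | Formula | Simulation |
|---|---|---|---|
| 0 | 1.0 | 5.0% | 4.8% |
| 0.1 | 1.3 | 8.6% | 8.3% |
| 0.3 | 1.9 | 15.5% | 15.6% |
| 0.5 | 2.5 | 21.5% | 21.6% |

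In the same simulations the patient-level any-AE chi-square held 5.2-5.5%, and a t-test on patients' total counts held 4.8-4.9%.

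**3. Events counted one by one.** If the variance of per-patient counts is D times the mean, the error is 2·(1 − Φ(1.96/√D)): 8.9%, 11.0% and 16.6% for D = 1.33, 1.5 and 2. Gamma-Poisson simulation with means of 0.67, 1.5 and 3 events per patient gave 8.9-9.1%, 10.8-10.9% and 16.2-16.6%. At D = 1 it gave 4.9-5.0%.

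**4. What Table 3 suggests.** In the study that 9.4 uses for its AE rate, the placebo rows are 5 + 4 + 2 + 7 = 18 reports from 9 of 27 participants. The least clustered allocation gives all nine two reports: mean 18/27 = 0.667, variance 9·4/27 − 0.667² = 0.889, ratio 1.33. On active treatment, 5 + 1 + 1 + 5 = 12 reports came from 8 participants. The least clustered allocation is four with two and four with one: variance 0.543, mean 0.444, ratio 1.22. If the cells are participants per type, independence between types would predict 27·(1 − 22/27·23/27·25/27·20/27) = 14.1 affected on placebo against 9 observed, and 10.4 against 8 on active. This is indirect evidence: it concerns types rather than visits, 27 per arm and 2-8 weeks.

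**5. The claimed gain in sensitivity.** For 1/3 v 2/3 on the any-AE scale, the patient-level chi-square has 81% power at every ICC. A cluster-valid comparison of patient totals (t-test) has 91%, 89%, 86% and 85% at ICC 0, 0.1, 0.3 and 0.5. The gain is real but falls from about 10 points under independence to about 4 at ICC 0.5.

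**The case against.** The strongest reply is that the plan already contains the remedy. The patient-level repeat is valid, the only power figure is patient-level, and 9.4 sets no alpha, hypothesis or stopping rule. With so many AE splits and no error control, event-level p-values are descriptive in practice. That limits the consequence. It does not make the event-level test correct, and 9.4 does not say which result leads if the two disagree.

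The last sentence of 9.4 is also not false in direction: combining AEs can detect a smaller excess, as step 5 shows, and the plan puts no number on the gain. It needs qualifying, not reversing.

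On Table 3, the contrast of 14 expected with 9 affected depends on the undefined row of other AEs. Using only the three named types, 9.6 affected placebo participants are expected against at most 9, and 6.6 on active against at most 8, which shows no clustering. This objection stands against that contrast. It does not reach the placebo ratio of at least 1.33, which needs only 18 reports from 9 of 27 participants.

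The remark on correlation in 9.1 explains why baseline-adjusted analysis is efficient; it does not warn about inflated error. It shows awareness of within-patient correlation and no more.

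Finally, Poisson regression with patient-robust standard errors is not exact at this sample size. Simulated error at 36 per arm is about 5.6-6.7%, and at 0.1 events per patient one arm has no events in about 5-16% of trials, so the model cannot be fitted. Permutation or descriptive reporting is safer for rare AEs.

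**Conclusion.** The concern holds. As written, the chi-square on summed or individually counted AEs is anti-conservative for any positive within-patient correlation, and nothing in 9.4 corrects it. Confidence is high for the direction only. The sizes in steps 2 and 3 rest on the assumed correlation or dispersion, a two-sided 5% level and complete follow-up, although the plan expects 20% dropout. With no within-patient correlation there is no inflation.

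The patient-level repeat for total AEs, an any-AE indicator combined over visits for each patient, and the 80% power for 33% v 67% are unaffected. The point should be corrected, but it does not threaten the trial's main conclusions.

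**What to change.** - Keep the patient-level chi-square as planned.
- Replace the chi-square on summed or individually counted AEs with an analysis that allows for clustering within patient: Poisson GEE with standard errors clustered on patient, negative binomial regression, or permutation of patients' total counts. Where events are sparse, report the counts without p-values.
- Reword the last sentence of 9.4 to say that any gain from combining AEs depends on within-patient correlation and is smaller than independent counting implies.
- State which level leads if the two disagree. That choice is the sponsor's, because the any-AE test can have less power: for 1/3 v 60% per patient it has about 61%, against 65-73% for a t-test on patient totals under the assumed model.

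The cost is analysis-plan wording and slightly more analysis, with no change to data collection or sample size. Intervals for event counts will be wider, and models may be unstable for rare AEs; permutation of patient totals avoids the model.
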